2.3.1.1 Intent-to-treat population

The intent-to-treat (ITT) population is the randomized population analyzed according to the treatment group allocated by randomization.

2.3.2 Safety population

The safety population is defined as randomized population who actually received at least 1 dose or part of a dose of the SC IMP, analyzed according to the treatment actually received

In addition:

- Nonrandomized but treated patients will not be part of the safety population; however, their safety data will be presented separately
- Randomized patients for whom it is unclear whether they took the IMP will be included in the safety population as randomized

- For patients receiving more than one SC IMP during the trial, the treatment group allocation for as-treated analysis will be the treatment group for which the patient received the majority of doses. In such cases, individual patient listings will be provided for each treatment group with treatment start and end date for each treatment exposed.

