HbA1c	X			X		X			X		X	X		
CRP ^l	X	X	X	X	X	X	X	X	X	X	X	X		
ESR ^l	X	X	X	X	X	X	X	X	X	X	X	X		
Urinalysis ^m	X													
Virology ⁿ	X													
Serum pregnancy test ^o	X													
Urine pregnancy test ^o		X		X	X	X	X	X	X	X	X	X		
12-lead ECG	X													
Serum sarilumab ^j		X	X	X		X	X		X ^p			X	X	
Anti-drug antibody ^j		X				X			X			X	X	
Genotyping and biomarkers^j														
Biomarkers-IL-6 and sIL-6R		X	X			X			X			X		
Blood for circulating immune cell phenotyping ^q		X		X					X					
Future Use of Samples for Circulating proteins (serum/plasma) ^r (optional)		X	X			X			X			X		

VISIT	V1	V2	V3	V4	V5	V6	V7	V8	V9	V10	V11	V12 (EOT)	V13	V14 (EOS)
DAY	D -42 to D -1	D1	D15 (±3)	D29 (±3)	D57 (±3)	D85 (±3)	D113 (±3)	D141 (±3)	D169 (±3)	D225 (±3)	D281 (±3)	D365 (±3)	D407 (±3)	D532 (±3)
WEEK		Wk 0	Wk 2	Wk 4	Wk 8	Wk 12	Wk 16	Wk 20	Wk 24	Wk 32	Wk 40	Wk 52	Wk 58	Wk 76
DNA ^S (optional)		X												
RNA ^S (optional)		X	X											

AE = Adverse event; ANA = Antinuclear antibodies; CRP = C-reactive protein; D = Day; DNA = Deoxyribonucleic acid; ECG = Electrocardiogram; EOT = End of treatment; EOS = End of study; EQ-5D-3L = EuroQol five-dimensional three-level questionnaire; ESR = Erythrocyte sedimentation rate; FACIT-Fatigue = Functional assessment of chronic illness therapy fatigue scale; GCA = Giant cell arteritis; GTI = Glucocorticoid toxicity index; HAQ-DI = Health assessment questionnaire disability index; HbA1c = Hemoglobin A1c; HBsAg = Hepatitis B surface antigen; HBcore Ab = Hepatitis B core antibodies; HCV = Hepatitis C virus; IL = Interleukin; IMP = Investigational medicinal product; IRT = Interactive response technology; MD-VAS = Physician global assessment of disease activity- visual analog scale; MRI = Magnetic resonance imaging; Pain VAS = Pain visual analog scale; PROs = Patient reported outcomes; Pt-VAS = Patient global assessment of disease activity – visual analog scale; RNA = Ribonucleic acid; SAE = Serious adverse event; SF-36v2 = Short form 36 version 2; TB = Tuberculosis; V = Visit; Wk = Week.

- a If ultrasound is being used as a diagnostic tool of GCA, the image needs to be submitted to the central reader for confirmation of eligibility.
- b Targeted physical examination: head, eyes, ears, neck and throat, skin, respiratory, cardiovascular, neurologic, lymphatic examinations and abdominal examination.
- c Last administration of sarilumab is at Week 50.

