Sarilumab will be administered in non-affected skin subcutaneously in the abdomen or thigh when self-injected or in upper arm (lateral side) when injected by a professional or a non-professional caregiver. It is preferred that SC injection sites be alternated between the 4 quadrants of the abdomen (except the navel or waist area) or the thigh (front and side). Each drug administration requires a single injection.

Patients and/or their non-professional caregivers will be trained to prepare and administer study drug at the baseline visit. This training must be documented in the subject's study file. The study staff should review the patient's self-administration technique at Visit 2 (Week 0). For doses not given at the study site, diaries will be provided to record information pertaining to those injections. If the patient is unable or unwilling to administer study drug, arrangements must be made for a qualified site personnel or a caregiver to administer study drug doses that are not scheduled to be given at the study site.

Dose regimen:

The IMP (sarilumab or matching placebo) should be administered every 14 days as per protocol IMP administration schedule, however an IMP administration time window of ± 3 days is permitted in exceptional circumstances (eg. Laboratory test result pending, or an ongoing adverse event (AE) or patient schedule difficulty). For subsequent IMP administrations the initial IMP administration schedule should be followed again (see [Table 1](#)).

Note: An interval of ≥ 11 days between 2 IMP doses must be maintained.

If the study visit is not performed at the site as scheduled, the dose will be administered as described above, either by the patient, qualified site personnel, and/or their caregiver(s).

On days when the patient has a study visit, the IMP will be administered after clinic procedures and blood collection.

Patients will be monitored for at least 30 minutes after each dose of sarilumab, or as per country specific requirements (eg, up to 2 hours) for any signs or symptoms of any medical events. In the case that the injection is administered by caregiver or self injection, patients should be instructed to monitor themselves for any signs or symptoms of any medical events.

The total duration of treatment is 52 weeks.

Dose modification/reduction:

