Sarilumab dose 200 mg may be reduced in response to elevated liver transaminases, neutropenia, and/or thrombocytopenia. The request for dose reduction will be managed via interactive response technology (IRT) and the sarilumab dose prior to and following the dose reduction will remain blinded to site and Sponsor (for patients in the sarilumab 150 mg or sarilumab matching placebo groups, the other treatment groups there will be only a sham dose reduction to maintain the blind). Please see [Section 10.7.2](#), [Section 10.7.3](#) and [Section 10.7.4](#) for further details. Once the dose is reduced, no further dose increase is permitted for the remainder of the study treatment period. Between the protocol-scheduled on-site visits, interim visits may be required for IMP dispensing. As an alternative to these visits, sarilumab or matching placebo may be supplied from the site to the patient via a Sponsor-approved courier company where allowed by local regulations and approved by the subject.

Post-trial access to sarilumab will be in compliance with all applicable national and local laws and regulations, including safety reporting obligations.

8.1.2 Prednisone or matching placebo:

Additional detail regarding the method of administration

Patients will be trained in the use of the weekly prednisone blister packs at the baseline visit. This training will include instruction on use of the blister packs in the appropriate order and use of the “spare” row of tablets/capsules in the case of loss of a tablet/capsule during dosing. The training must be documented in the patient’s study file.

All patients will receive prednisone (at doses of 60 mg/day or less) and/or matching placebo (double-blind prednisone tapering phase only) following different standardized prednisone-taper regimen for treatment of GCA depending on the assigned treatment group. In the open-label phase all patients will receive prednisone tablets while in the double-blind prednisone tapering phase patients will receive encapsulated prednisone tablets in blinded packaging.

There will be 2 standardized CS-taper regimens defined:

- Up to 26 week taper (Group A, Group B and Group C).

- Up to 52 week taper (Group D).

There will be 2 phases for each prednisone taper regimen:

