11.3.2 Safety population

Safety population: all randomized patients who have received at least one dose or part of a dose of the study medication (IMP) analyzed according to the treatment they have actually received.

In addition:

- Nonrandomized but treated patients will not be part of the safety population, but their safety data will be presented separately.
- Randomized patients for whom it is unclear whether they took the study medication will be included in the safety population as randomized.
- For patients receiving more than 1 study treatment during the trial, the treatment group allocation for as-treated analysis will be the treatment for which the patient received the majority of doses.

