- All TEAEs by maximal severity, presented by primary SOC and PT, showing number (%) of patients with at least one TEAE by severity (ie, mild, moderate, or severe), sorted by sorting order defined above.

Analysis of all treatment emergent serious adverse event(s)

- All treatment-emergent SAEs by primary SOC, HLG, HLT, and PT, showing number (%) of patients with at least one serious TEAE, sorted by SOC internationally agreed order. The other level (HLG, HLT, PT) will be presented in an alphabetic order.
- All treatment-emergent SAEs by primary SOC and PT, showing number (%) of patients with at least one TEAE
- All treatment-emergent SAEs by primary SOC, showing number (%) of patients with at least one TEAE, sorted by internationally agreed order of primary SOC

Analysis of all treatment-emergent adverse event(s) leading to treatment discontinuation

- All TEAEs leading to treatment discontinuation, by primary SOC, HLG, HLT, and PT, showing number (%) of patients sorted by SOC internationally agreed order. The other level (HLG, HLT, PT) will be presented in an alphabetic order.
- All TEAEs leading to treatment discontinuation, by primary SOC and PT, showing number (%) of patients with at least one TEAE
- All TEAEs leading to treatment discontinuation, by primary SOC, showing number (%) of patients with at least one TEAE, sorted by internationally agreed order of primary SOC

Analysis of all treatment-emergent adverse event(s) leading to dose reduction

- For the management of pre-defined laboratory abnormalities, sarilumab dose can be reduced to 150 mg q2w. All treatment-emergent adverse events leading to dose reduction, by primary SOC, HLG, HLT and PT, showing the number (%) of patients, sorted by the sorting order defined above

Analysis AESI

- Summaries of AESI defined by the search criteria:
 - All treatment-emergent AESIs, by AESI category and PT, showing number (%) of patients, sorted by decreasing incidence of PT within each AESI category.
 - Within each treatment-emergent AESI category, at a minimum the data display will include:
 - Overview summary
 - Treatment duration summary
 - Incidence by patient and by event

- Serious TEAEs
- TEAEs leading to treatment discontinuation
- TEAEs leading to death
- Possibly related TEAEs

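### The majority-of-doses rule for the safety groups has no exception for the permitted 200-to-150 mg reduction, so patients reduced early would be tabulated under 150 mg

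*SAP*

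**What the plan says.** SAP 2.3.2 analyses safety by treatment actually received. For a patient with more than one subcutaneous IMP, "the treatment group allocation for as-treated analysis will be the treatment group for which the patient received the majority of doses". The sentence after it adds individual listings with the start and end dates of each treatment. Protocol 11.3.2 is triggered by receipt of more than one study treatment and reads "the treatment group allocation for as-treated analysis will be the treatment for which the patient received the majority of doses". Neither section mentions dose reduction or ties.

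The protocol allows a real change of dose in one arm only. Section 8.1.1 states: "Sarilumab dose 200 mg may be reduced in response to elevated liver transaminases, neutropenia, and/or thrombocytopenia". It also states: "Once the dose is reduced, no further dose increase is permitted for the remainder of the study treatment period". For the 150 mg and placebo groups "there will be only a sham dose reduction to maintain the blind". Sections 10.4.1 and 10.7.2 to 10.7.4 leave it to the investigator whether treatment resumes at the same or the lower dose after the abnormality recovers.

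SAP 2.4.5 runs all safety analyses on the safety population unless otherwise specified, and SAP 2.4.5.1 takes that population within each treatment group as the denominator for adverse event percentages. The planned outputs include an analysis of "all treatment-emergent adverse event(s) leading to dose reduction".

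**The concern.** The four groups are defined by dose, so a patient switched from 200 mg to 150 mg has received the treatments of two groups. The majority rule then decides the column from what happened after randomization. By this route patients can move only from 200 mg to 150 mg, and the cause of the move is the kind of laboratory toxicity that the tables are meant to compare between doses. No text attributes an event to the dose being taken at onset, so the whole patient record moves, including the abnormality that arose on 200 mg. The denominators move too.

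At stake is the descriptive dose comparison for raised ALT, neutropenia and thrombocytopenia: 200 mg would look cleaner and 150 mg worse than their randomized groups. Groups of about 28 and 14 are small enough for one or two patients to be visible. Efficacy analyses by randomized group are unaffected.

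**Working it through.** **Inputs**
- Dosing interval: the subcutaneous product "should be administered every 14 days as per protocol IMP administration schedule" (protocol 8.1.1).
- Last dose: "Last administration of sarilumab is at Week 50" (protocol 1.2, footnote c).
- On-treatment hematology and chemistry before Week 52: Weeks 4, 12, 24 and 40 (protocol 1.2; SAP 2.1.4.3).
- Interruption before resuming: at least one dose is missed, and more than 31 consecutive days counts as permanent (protocol 10.4.1). Taken here as 1 or 2 missed doses, which is an assumption.
- Randomized patients: 83 at 2:1:1:2. All had the opportunity for at least 24 weeks of treatment, and about 36 for 52 weeks (SAP 1.3).

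**Group sizes.** 83 × 2/6 = 27.67 and 83 × 1/6 = 13.83. These agree with the 28 (Group A) and 14 (Group B) in SAP Table 1, used here as approximate safety denominators.

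**Doses in a full course.** Weeks 0, 2, …, 50 give 50/2 + 1 = 26 doses.

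**Doses at each strength.** Let T be the number of doses in the patient's schedule. The 200 mg count is the doses before the triggering visit, plus one if the visit-day dose was given before the result was known. The 150 mg count is T minus the 200 mg count minus the missed doses (1 or 2). Example for Week 12 in a full course: 6 doses before the visit (Weeks 0 to 10), or 7 with the visit-day dose; then 26 − 6 − 1 = 19 down to 26 − 7 − 2 = 17 at 150 mg.

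| Last dose (T) | Trigger visit | 200 mg doses | 150 mg doses | Column under the rule |
|---|---|---|---|---|
| Week 50 (26) | Week 4 | 2–3 | 21–23 | 150 mg |
| Week 50 (26) | Week 12 | 6–7 | 17–19 | 150 mg |
| Week 50 (26) | Week 24 | 12–13 | 11–13 | 150 mg (12 v 13), tie (12 v 12) or 200 mg (13 v 12, 13 v 11) |
| Week 50 (26) | Week 40 | 20–21 | 3–5 | 200 mg |
| Week 34 (18) | Week 12 | 6–7 | 9–11 | 150 mg |
| Week 28 (15) | Week 12 | 6–7 | 6–8 | 150 mg (6 v 8, 6 v 7), tie (7 v 7) or 200 mg (7 v 6) |
| Week 22 (12) | Week 4 | 2–3 | 7–9 | 150 mg |
| Week 22 (12) | Week 12 | 6–7 | 3–5 | 200 mg |

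The threshold is therefore half of the doses actually received, not a fixed dose number.

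**Effect on the columns.** The documents give no number of reductions. Assume k = 1 to 4 early-reduced patients who all move, and no such event among the 14 randomized to 150 mg. Kept as randomized, the columns show k/28 and 0/14; under the rule, 0/(28 − k) and k/(14 + k).

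| k | As randomized: 200 mg v 150 mg | Majority rule: 200 mg v 150 mg |
|---|---|---|
| 1 | 1/28 (3.6%) v 0/14 | 0/27 v 1/15 (6.7%) |
| 2 | 2/28 (7.1%) v 0/14 | 0/26 v 2/16 (12.5%) |
| 3 | 3/28 (10.7%) v 0/14 | 0/25 v 3/17 (17.6%) |
| 4 | 4/28 (14.3%) v 0/14 | 0/24 v 4/18 (22.2%) |

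**The case against.** The best defence is that the rule was never meant for dose reduction. The SAP trigger is more than one subcutaneous IMP. Protocol Table 1 lists sarilumab as a single product with both syringe strengths, and the interruption rules describe a reduction as the same product resumed at a lower dose. On that reading the rule still has work to do: SAP 2.2.1 foresees a patient dispensed a kit other than the one randomized, for example both sarilumab and placebo. This is a possible reading of the SAP. It fits the protocol less well, because the trigger there is more than one study treatment and the groups are defined by dose. A programmer applying the text as it stands could reasonably move these patients.

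Three further points limit the reach. Reduction is optional. The most severe abnormalities require permanent discontinuation (protocol 10.4.3), so without a prior reduction those events stay under 200 mg. The listings let a reader trace each case, although they leave the summary columns unchanged.

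Four stronger readings that a reader might infer are not supported:
- That every reduction before the 13th dose moves the patient. A Week 12 reduction with the last dose at Week 22 stays under 200 mg, and a full course can tie at 12 v 12.
- That the dose–safety comparison will be reversed. The order reverses in the illustration only because of the assumed counts.
- That any entry under 150 mg in the dose-reduction table is an anomaly. Sham reductions can legitimately appear there; the difficulty is only that moved patients' real reductions would be mixed with them.
- That keeping reduced patients under 200 mg has no drawback. Events that arise on 150 mg would then be counted under 200 mg.

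**Conclusion.** The point holds as a gap in a stated rule. Read literally, SAP 2.3.2 and protocol 11.3.2 place a 200 mg patient with more 150 mg than 200 mg doses in the 150 mg safety column, including the toxicity that prompted the reduction. In a full course this applies to Week 4 and Week 12 triggers. A Week 24 trigger can move, tie or stay, with no tie-break given, and a Week 40 trigger stays. With a last dose at Week 22, only the Week 4 trigger moves.

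The size is unknown. The illustrated range rests on the assumed 1 to 4 early cases, no such event among patients randomized to 150 mg, and the estimated group sizes of 28 and 14; with no early reductions the effect is zero. All safety analyses are descriptive, so no formal inference is affected. The change should still be made, because the possible misallocation is driven by the outcome being tabulated.

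**What to change.** Add to SAP 2.3.2:
- A dose reduction permitted by the protocol does not change the safety group; the patient stays under sarilumab 200 mg in the summary tables.
- The majority-of-doses rule applies only to dispensing errors, with a stated tie-break (for example, the randomized group).
- Events with onset after a reduction are flagged in the listings, or a supplementary summary by dose at onset is added.

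Because this narrows protocol 11.3.2, record it in SAP 1.6 among the changes from the protocol.

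The cost is a few sentences and one flag. The drawback is small: some events arising on 150 mg are counted under 200 mg, which the flag or supplementary summary makes visible. Only reporting changes; dosing and patient management are untouched.

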2.3.3 Pharmacokinetics and ADA populations

The PK population will consist of all patients in the safety population with at least one post-dose, non-missing serum sarilumab concentration value. The ADA population will consist of all patients in the safety population with at least one post-dose, evaluable ADA sample. Patients will be analyzed according to the treatment actually received.

2.4 STATISTICAL METHODS

2.4.1 Demographics and baseline characteristics

Continuous data will be summarized using the number of available data, mean, standard deviation (SD), median, minimum, and maximum for each treatment group. Categorical and ordinal data will be summarized using the number and percentage of patients in each treatment group.

Parameters will be summarized based on the randomized populations.

Parameters described in [Section 2.1.1](#) will be summarized by treatment group and overall using descriptive statistics.

Medical and surgical history will be summarized by SOC and PT sorted by internationally agreed order of SOC and by the decreasing frequency of PT within SOC in total group (including all the randomized patients). P-values on demographic and baseline characteristic data will not be calculated.

No specific description of the safety parameters will be provided at baseline. If relevant, the baseline values will be described along with each safety analysis.

2.4.2 Prior or concomitant medications

The prior and concomitant medications will be summarized based on the randomized populations as follows:

- Prior medications discontinued before the first dose of IMP in the DB period
- Prior medications that continued at the time of the first dose of IMP in the DB period
- Concomitant medications

Medications will be summarized by treatment group according to the WHO-DD dictionary, considering the first digit of the anatomic category (ATC) class (anatomic category) and the

generic names. All ATC codes corresponding to a medication will be summarized. Patients will be counted once in each ATC category (anatomic or therapeutic) linked to the medication; therefore, patients may be counted several times for the same medication.

In addition, the following summaries will also be provided:

- Vaccines (prior and concomitant vaccines will be summarized separately)
- Other prior DMARDs/immunosuppressive agents taken since diagnosis of GCA and discontinued before the first dose of IMP

The table for prior medications will be sorted by decreasing frequency of anatomic category followed by all other generic names based on the overall incidence across treatment groups. In case of equal frequency regarding anatomic categories (respectively, generic names), alphabetical order will be used.

The tables for concomitant medications will be sorted by decreasing frequency of anatomic category followed by all other generic names based on the incidence of the total group (including all the randomized patients). In case of equal frequency regarding anatomic categories (respectively, generic names), alphabetical order will be used.

2.4.3 Extent of investigational medicinal product exposure and compliance

The extent of SC IMP exposure and compliance will be assessed and summarized by actual treatment group within the safety population ([Section 2.3.2](#)).

2.4.3.1 Extent of investigational medicinal product exposure

The extent of SC IMP exposure will be assessed by the duration of SC IMP exposure and actual dose information.

The duration of SC IMP exposure is defined as last DB dose date – first DB dose date +14 days, regardless of unplanned intermittent discontinuations (see [Section 2.5.3](#) for calculation in case of missing or incomplete data).

Duration of SC IMP exposure will be summarized descriptively as a quantitative variable (number, mean, SD, median, minimum, and maximum). In addition, duration of treatment exposure will also be summarized categorically by numbers and percentages for each of the following categories and cumulatively according to these categories: ≤ 4 weeks, >4 and ≤ 8 weeks, >8 and ≤ 12 weeks, >12 and ≤ 16 weeks, >16 and ≤ 20 weeks, >20 and ≤ 24 weeks, >24 and ≤ 32 weeks, >32 and ≤ 40 weeks, >40 and ≤ 52 weeks and >52 weeks.

Additionally, the cumulative duration of treatment exposure, defined as the sum of patients' duration of treatment exposure and expressed in patient years, will be provided.

